#### 10 STATISTICAL CONSIDERATIONS

#### 10.1 STATISTICAL AND ANALYTICAL PLANS

A statistical analysis plan (SAP) will be created prior to the final analysis being performed for the study and will provide further detail to the statistical techniques that will be used for the analysis of the study endpoints.

# 10.2 STATISTICAL HYPOTHESES

The statistical hypothesis for the superiority of the cochlear implant in CNC word score and AzBio sentence score at six months, compared to pre-operative performance with appropriately fit hearing aids by a margin of 10 percentage points can be written as follows:

 $H_o$ :  $\mu_{\Delta} \leq 10$ 

 $H_a$ :  $\mu_{\Delta} > 10$ ,

where  $\mu_{\Delta}$  is the mean change in the CNC word score or AzBio sentence score from baseline to 6-months and 10 is the superiority margin representing a 10 percentage point change in mean CNC word score or AzBio sentence score.

#### 10.3 ANALYSIS DATASETS

Analysis datasets will be created using SAS format. These SAS datasets will be used for the final analysis of the study and will be archived at the end of the study.

#### 10.4 DESCRIPTION OF STATISTICAL METHODS

# 10.4.1 GENERAL APPROACH

Continuous variables will be summarized using mean, median, inter-quartile range, minimum, and maximum values. Categorical variables will be summarized using counts and percents. Testing of the primary endpoint will be done at the 0.025 level of significance. Additional detail regarding the statistical methods will be included in the SAP.

#### 10.4.2 ANALYSIS OF THE PRIMARY EFFECTIVENESS ENDPOINT

The mean change in CNC word score or AzBio sentence score from baseline to 6-months will be summarized as a continuous variable using the descriptive statistics described in section 10.4.1. Additionally, a one-sided, paired t-test comparing the mean change in CNC word score or AzBio sentence score to the superiority margin of 10 will be performed and the corresponding p-value will be reported. A p-value less than 0.025 will result in rejection of the null hypothesis indicating that the mean change in CNC word score or AzBio sentence score was greater than 10 percentage points.

# 10.4.3 ANALYSIS OF THE SECONDARY ENDPOINT(S)

Secondary endpoints will not be formally tested but will be summarized using appropriate descriptive statistics. Details of the methods used will be laid out in the SAP.

The number and percentage of subjects performing similarly or better on AzBio at 6 months postoperatively compared to the pre-operative aided condition will be summarized. Responses from the APHAB and SSQ questionnaires will also be summarized descriptively. The number and percentage of subjects with complete hearing preservation, partial hearing preservation, minimal hearing preservation, and loss of hearing (according to the HEARRING classification) will also be summarized. Adverse events will be summarized by the number and percent of subjects experiencing adverse events.

#### 10.4.4 SAFETY ANALYSES

Adverse events will be listed and summarized based on the type and severity of the event.

# 10.4.5 ADHERENCE AND RETENTION ANALYSES

Adherence will be defined as those subjects who adhered to all protocol requirements. A per protocol analysis population will be defined in the SAP and the primary endpoint of change in CNC word score will be assessed.

Subjects lost to follow-up or terminated early for other reasons will be tabulated and summarized. For those subjects without a 6 month follow-up visit, the six month CNC word score or AzBio sentence score will be imputed using last observation carried forward. Only a small number of subjects are expected to be lost and benefit from the implant should be immediate making this imputation method reasonable.

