#### 4.2 STUDY ENDPOINTS

#### 4.2.1 PRIMARY ENDPOINTS

The co-primary endpoint will be the comparison of CNC word score with the cochlear implant at six months post-activation to the pre-operative aided CNC word score in the implanted ear. Improvement will be defined as equal to or greater than 10 percentage points. Testing will occur in the soundfield at 60 dB SPL. The second co-primary endpoint will be the comparison of AzBio sentence score in noise with the cochlear implant at six months post-activation to the pre-operative aided AzBio score in the implanted ear. Improvement will be defined as equal to or greater then 10 percentage points. Testing will occur in the soundfield at 60 dB SPL with a signal-to-noise ratio of +10 dB SNR.

Study success will be determined based on the analysis of both co-primary endpoints. In order for the study to be considered successful, both co-primary endpoints must be met.

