#### 10.4.10 TABULATION OF INDIVIDUAL RESPONSE DATA

An overall list of each subject with his or her CNC word score and AzBio sentence score at baseline, 1 month, 3 months, 6 months, and 12 months along with the change in CNC word score and AzBio sentence score from baseline to 6 months, will be provided.

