# 10.4.11 EXPLORATORY ANALYSES

Exploratory analyses in the form of a repeated measures analysis will be done for the primary, secondary, and subjective questionnaire scores to characterize any changes over time.

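### Carrying the last score forward for every subject without a 6-month visit covers neither scores still changing nor loss of the device, so the co-primary mean can be biased in either direction

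*Combined protocol and SAP*

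**What the plan says.** Section 10.4.5 applies to subjects without a 6-month follow-up visit. For them, "the six month CNC word score or AzBio sentence score will be imputed using last observation carried forward". The reason given is: "Only a small number of subjects are expected to be lost and benefit from the implant should be immediate making this imputation method reasonable". The sentence before the rule covers subjects lost to follow-up and those terminated early for other reasons. No reason for absence is treated differently.

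Section 10.2 defines the tested parameter: it "is the mean change in the CNC word score or AzBio sentence score from baseline to 6-months". Section 10.4.2 tests it with "a one-sided, paired t-test comparing the mean change in CNC word score or AzBio sentence score to the superiority margin of 10", at one-sided 0.025. Section 4.2.1 describes the second co-primary endpoint as the "comparison of AzBio sentence score in noise with the cochlear implant at six months post-activation to the pre-operative aided AzBio score", and requires that "both co-primary endpoints must be met".

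Three other provisions bear on the point. Section 10.4.11 says: "Exploratory analyses in the form of a repeated measures analysis will be done for the primary, secondary, and subjective questionnaire scores". Section 10.4.10 promises, with the later visits as well, "An overall list of each subject with his or her CNC word score and AzBio sentence score at baseline". Section 10.4.5 also plans a per-protocol analysis, but names only CNC for it. Sections 10.1 and 10.4.1 defer further detail to a separate SAP, which is not in these documents.

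**The concern.** The trial has one arm, so no control group offsets an imputation bias. It passes directly into the mean that is compared with 10. Immediate benefit is an argument about when benefit starts. It does not show that a score at 1 or 3 months has reached its 6-month level, and it says nothing about a subject who no longer has a working implant.

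The two gaps act in opposite directions:

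- **Downward.** A subject lost while still improving is held at too low a score. A subject with no score after activation would have a change of 0 if the baseline is carried; the section does not say whether it is.
- **Upward.** Section 8.1.3 gives infection or device failure leading to explantation as an example of a serious event. Section 5.4.1 lets an adverse event end participation, and Section 5.4.2 collects no data after withdrawal. A subject tested at 1 or 3 months, then explanted and withdrawn before 6 months, contributes a change measured with a working implant. This overstates the mean if the target is all implanted subjects. Section 4.2.1 defines the endpoints with the implant in use and does not say how device loss counts, so the target itself is open.

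At stake is a primary result that rests on an unstated rule for device loss and on an assumption of no change between visits.

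**Working it through.** **Inputs.** From Section 10.5: n = 50, one-sided alpha 0.025, margin 10, CNC change 24.4 (SD 21.9), AzBio change 15 (SD 8.4), stated power about 90% and 83%. The critical t on 49 df is 2.010. The documents give no explant rate. The number of explants, k = 1 to 3, and their true change of 0 are assumptions.

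**1. The plan's own power.** For the paired t-test, power = P(T > 2.010), where T is noncentral t with 49 df and noncentrality (change − 10)/(SD/√50).

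- CNC: 14.4/(21.9/√50) = 14.4/3.097 = 4.65, power 99.5%.
- AzBio: 5/(8.4/√50) = 5/1.188 = 4.21, power 98.5%.

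These are not the stated figures. With each SD multiplied by √2 the same formula gives 89.7% and 83.1%, which match; a two-sample formula with 50 per arm also comes close (90.2% and 83.8%). The SD of the AzBio change is therefore uncertain, so AzBio results below are given for 8.4 and for 8.4 × √2 = 11.88.

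**2. Shift per subject at the planned effects.** An explant carried at the full planning mean instead of 0 raises the tested mean by 24.4/50 = 0.49 points (CNC) or 15/50 = 0.30 points (AzBio). An early loss set to 0, when the true change is the planning mean, lowers it by the same amounts.

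**3. Worst-case error at the margin.** Let the true mean over all 50 implanted subjects be 10, with k explants at 0. The mean with a working implant is then m = 500/(50 − k). If all 50 analysed values have mean m (full carry, no downward losses), the noncentrality is (m − 10)/(SD/√50).

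| k | m | CNC, SD 21.9 | AzBio, SD 8.4 | AzBio, SD 11.88 |
|---|---|---|---|---|
| 1 | 10.204 | 0.029 | 0.037 | 0.033 |
| 2 | 10.417 | 0.034 | 0.053 | 0.043 |
| 3 | 10.638 | 0.039 | 0.076 | 0.056 |

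For example, AzBio with k = 2 and SD 8.4 has noncentrality 0.417/1.188 = 0.351 and error 0.053.

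**4. Relaxing the worst case** (simulation, k = 2, Section 10.5 SDs).

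- Carried score averaging 70% or 50% of m: 0.031 or 0.029 (CNC); about 0.042 or 0.036 (AzBio).
- Full carry plus 1 or 2 subjects with working devices lost early and set to 0: 0.028 or 0.024 (CNC); about 0.034 or 0.020 (AzBio).

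**5. Power at the planned effects if explants count as 0** (simulation, t-test).

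| Explants at 0 | CNC, SD 21.9 | AzBio, SD 8.4 | AzBio, SD 11.88 |
|---|---|---|---|
| 0 | 99.5% | 98.5% | 83% |
| 1 | about 99% | about 97% | about 78% |
| 2 | about 99% | about 95% | about 73% |

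With the planning means and Section 10.5 SDs taken as observed values, AzBio stays significant with up to 7 of 50 subjects at 0 and fails at 8 (t = 1.94). CNC is still significant at 15, the largest number tried.

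**The case against.** The upward route needs four things together: device loss, an earlier test at 1 or 3 months, loss before 6 months, and no 6-month visit. Section 2.2.1 calls device failure rare, Section 10.4.5 expects few losses, and explantation is not itself a listed withdrawal reason. The endpoints are defined with the implant in use, so an all-implanted target is one possible reading and not a stated one. Further detail is left to an SAP that could add sensitivity analyses, and the visit-level listing would let a reader re-run the result. All of this stands, and it limits the size of the point.

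It does not remove the point. The method is already fixed in Section 10.4.5, the repeated-measures analysis is only exploratory, and neither it nor the listing alters the primary test.

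Two stronger readings are tempting. A reader might infer that every missing 6-month score is imputed. The trigger is a missing visit, so a subject who attends without a score, or attends after explantation or re-implantation, falls outside the rule, and nothing says how that subject counts. A reader might also infer that the rule favours success. Losses during improvement act the other way, and step 4 shows that two early losses more than offset two explants.

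**Conclusion.** The point holds as a weakness in the primary missing-data rule, with unknown net direction. The justification covers neither further change after 1 or 3 months nor device loss. That imputed values enter the t-test is the natural reading, because they replace the score it uses and Section 10.3 defines no analysis population that would exclude them; the text does not say so outright.

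The errors in step 3 are upper-end illustrations. They require an all-implanted target, a true mean of exactly 10, explants at exactly 0, full carry and no downward losses. They are also per endpoint. A reader might take 0.076 as the trial's false-positive rate, but both endpoints must succeed, so this would be approached only if CNC were almost certain to pass and the AzBio SD were 8.4. At the planned effects one or two explants rarely change the conclusion. The change is worth making because it is cheap, not because the planned result is in doubt.

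**What to change.** Amend Section 10.4.5, and carry the change into the SAP, for both co-primary endpoints:

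1. Replace last observation carried forward with a likelihood-based repeated-measures model over the scheduled visits, testing the 6-month mean change against 10. This promotes the analysis in Section 10.4.11. Multiple imputation from the other visits' scores is an alternative. Keep last observation carried forward as a sensitivity analysis.
2. Either method alone would still predict a working-implant score after device loss. State whether the estimand covers all implanted subjects. Pre-specify an analysis in which subjects known to be explanted or to have a failed device, and without a 6-month visit, count as no improvement (change 0). Zero is a judgement, since loss of residual hearing could leave the ear below baseline, so add a below-baseline or tipping-point sensitivity analysis. Say how a subject who attends at 6 months after device loss or re-implantation is counted.
3. As a separate matter, run the per-protocol analysis for AzBio as well as CNC.

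Visits and tests do not change. The cost is a protocol text change needing IRB approval (Section 13.2), modest programming, and a less favourable result if explants occur. Step 5 gives the size: small under the Section 10.5 SDs, but AzBio power would fall from 83% to about 78% or 73% with one or two explants if the SD of change is 8.4 × √2. Those figures are for a t-test with zeros, not for the proposed model. Device status may also be unknown for some subjects lost to follow-up, which is why item 2 is limited to known device loss.

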#### 10.4.6 BASELINE DESCRIPTIVE STATISTICS

Baseline descriptive statistics will be summarized and reported for all subjects with available baseline data. All demographic and medical history information will be tabulated and presented as described in section 10.4.1 above.

#### 10.4.7 PLANNED INTERIM ANALYSES

No interim analyses are planned for this study.

#### 10.4.8 ADDITIONAL SUB-GROUP ANALYSES

The change in CNC word score and AzBio sentence score will be summarized by electrode array. Those subjects receiving the SYNCHRONY +FLEXSOFT electrode array will form one group while those receiving SYNCHRONY +FLEX will form the other. No formal statistical comparison will be done between these two groups.

Likewise, the change in CNC word score and AzBio sentence score will also be summarized by sex. Again, no formal statistical testing will be done.

# 10.4.9 MULTIPLE COMPARISON/MULTIPLICITY

Both co-primary enpdoints are being tested at the 0.025 level of significance. Testing at this level for the individual endpoint wil control the overall Type I error rate to the 0.05 level.

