#### 10.5 SAMPLE SIZE

The sample size estimate is based on attaining adequate power to test the co-primary endpoint of the study. The hypothesis test is a paired one-sample T-test of superiority of the mean change in CNC word score from baseline to 6-months with a superiority margin of 10 percentage points. The test will be performed at the one-sided alpha = 0.025 level. A sample size of 50 would yield approximately 90% power assuming the true change in mean CNC word score is 24.4 with a standard deviation of 21.9.

The paired T-test will also be used to test for superiority of the mean change in AzBio sentence score from baseline to 6-months with a superiority margin of 10 percentage points. The test will be performed at the one-sided alpha = 0.025 level. A sample size of 50 would yield approximately 83% power assuming the true change in mean AzBio sentence score is 15 with a standard deviation of 8.4.

The estimates used for the sample size calculation came from the results for the Electric-Acoustic System (EAS) Investigational pivotal trial.

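### Does the overall Type I error of 0.05 in section 10.4.9 conflict with the rule that both co-primary endpoints must succeed?

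*Combined protocol and SAP*

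**What the plan says.** Four places in the combined protocol and SAP bear on this.

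- **Section 4.2.1 (success rule):** "In order for the study to be considered successful, both co-primary endpoints must be met".
- **Section 10.4.9 (multiplicity):** "Both co-primary enpdoints are being tested at the 0.025 level of significance", followed by "Testing at this level for the individual endpoint wil control the overall Type I error rate to the 0.05 level". It gives no reasoning and does not say whether 0.05 is one-sided or two-sided.
- **Section 10.5 (sample size), for each endpoint:** "The test will be performed at the one-sided alpha = 0.025 level". Section 10.4.2 also specifies a one-sided paired t-test with a threshold of 0.025.
- **Section 10.4.2 (primary analysis):** the two endpoints are joined by *or*, both in the test, "comparing the mean change in CNC word score or AzBio sentence score to the superiority margin of 10 will be performed", and in the conclusion drawn from a small p-value, "the mean change in CNC word score or AzBio sentence score was greater than 10 percentage points".

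Section 10.4.7 plans no interim analysis, so no alpha is spent elsewhere.

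**The concern.** Splitting 0.05 into two tests at 0.025 is the usual device when a win on either endpoint is enough. When both must win, no split is needed, and the overall error is bounded by the level of a single test, here 0.025 one-sided. Section 10.4.9 therefore seems to quote the error rate of a rule that section 4.2.1 does not use, and the *or* in section 10.4.2 can be read the same way.

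If the document really held two decision rules, a split result would be open to dispute. A sponsor seeking expanded labeling could point to one section to claim success on CNC alone, with a one-sided error of up to 0.05 across the two endpoints, while another section said the study had failed. Even without that, a stated overall alpha of twice the achievable maximum would look like an arithmetic slip.

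**Working it through.** **Inputs.** Per-test level 0.025, one-sided (10.4.2, 10.4.9, 10.5). Margin 10 points (10.2). n = 50; assumed change and SD 24.4 and 21.9 for CNC, 15 and 8.4 for AzBio (10.5), which is 14.4 and 5 points above the margin. Success needs both endpoints (4.2.1).

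**Step 1: reproduce 0.05.** Three routes reach it, or nearly so:

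- Bound on at least one false rejection across the two tests: 0.025 + 0.025 = 0.05.
- The same quantity if the tests were independent: 1 − 0.975² = 0.0494.
- One-sided 0.025 restated on the two-sided scale: 2 × 0.025 = 0.05.

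The text does not say which was meant.

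**Step 2: error under the both-required rule.** A false success needs at least one null hypothesis to be true and both to be rejected. The probability of rejecting both cannot exceed the probability of rejecting the true one, so

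P(false success) ≤ max(0.025, 0.025) = 0.025.

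If both nulls hold at the margin and the tests are independent, it is 0.025² = 0.0006.

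**Step 3: simulation check.** Paired t-tests, n = 50, bivariate normal changes, critical value at 49 degrees of freedom, 80,000 replicates per setting. The correlation between the two changes is not given in the documents, so a range is shown.

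| True state | Rule | Corr. 0 | Corr. 0.5 | Corr. 0.8 |
|---|---|---|---|---|
| Both at the margin | both must win | 0.0006 | 0.0044 | 0.011 |
| CNC at the margin, AzBio 5 above | both must win | 0.0249 | 0.0242 | 0.0252 |
| AzBio at the margin, CNC 14.4 above | both must win | 0.0242 | 0.0253 | 0.0252 |
| Both at the margin | either wins | 0.0495 | 0.046 | 0.0397 |

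The Monte Carlo standard error at 0.025 is √(0.025 × 0.975 / 80,000) = 0.0006, so the worst case is 0.025 to within simulation noise. The either-wins row describes a rule the protocol does not use.

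**Step 4: what *or* means.** Section 10.2 writes one hypothesis pair with one parameter, which "is the mean change in the CNC word score or AzBio sentence score from baseline to 6-months", and one margin: "10 is the superiority margin representing a 10 percentage point change in mean CNC word score or AzBio sentence score". There, *or* applies a single template to each endpoint in turn. Section 10.4.5 uses the same construction for imputing a missing six-month score, where a reading that one endpoint suffices makes no sense. Section 10.4.2 follows this pattern: it says when a null hypothesis is rejected and does not mention study success.

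**Step 5: possible outcomes under the plan as written.**

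- Both p-values below 0.025: success.
- Exactly one below 0.025: not a success, by section 4.2.1.
- Neither below 0.025: not a success.

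The 0.05 in section 10.4.9 is not used in any of these.

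**The case for a change.** The best case for an edit is that section 10.4.9 is where a reader looks for the multiplicity rule, yet it never says that both tests must reject or that no adjustment is needed. Its sentence moves from the individual endpoint to the overall rate, which is a step across endpoints rather than from one tail to two, and the hypotheses in section 10.2 have only one error direction. Nearby text is untidy as well: section 10.4.1 speaks of a single primary endpoint, and section 10.4.5 names only CNC for the per-protocol analysis. Sections 10.1 and 10.4.1 leave detail to a SAP still to be written, so loose wording could carry forward into a labeling submission.

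Part of this stands. The 0.05 is looser than the rule delivers, and a line saying that both must reject, with overall one-sided error at most 0.025, would read better. *Each of* would be clearer than *or* in section 10.4.2.

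The stronger claims do not stand. Either-wins reasoning is inferred, since the section gives none. A true upper bound is not a figure wrong by a factor of two. There is no second decision rule, because section 4.2.1 alone defines success and does so without ambiguity. A claim on one endpoint after a split result is already ruled out there.

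**Conclusion.** The concern does not call for a change, because an edit would bring no gain beyond tidier wording. The one-sided chance of false study success is at most 0.025, and the stated 0.05 is a valid but loose ceiling. The discrepancy runs in the safe direction: the plan claims less protection than it has. Rewording would alter no test, margin, threshold, sample size or success decision, and an analyst who follows sections 4.2.1 and 10.4.2 as written reaches the right conclusion.

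This rests on two assumptions. The first is that section 4.2.1 governs success, which is the only reading its text allows. The second is that each paired t-test holds its nominal level at n = 50. The 0.025 bound does not depend on the correlation between endpoints or on the planning SDs; these only determine how far below 0.025 the actual error falls.
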